### **7.2.3 Compound Background**

Liso-cel is a genetically modified autologous cell-based product consisting of purified CD8+ and CD4+ T cells, in a defined composition, that have been [REDACTED] transduced ex vivo using a replication-incompetent lentiviral vector expressing a CD19-specific CAR. The CD19-specific CAR consists of an scFv binding domain derived from a murine CD19-specific monoclonal antibody (mAb) (FMC63) and the 4-1BB and CD3 $\zeta$  co-stimulatory/signaling domains. [REDACTED]

In vitro and in vivo studies have demonstrated the ability of liso-cel to proliferate, produce cytokines, and exhibit antitumor activity against CD19-positive cell lines and in tumor-bearing mice. The drug product is provided as CD8+ and CD4+ frozen T cell suspensions, which are thawed and infused [REDACTED]. Administration of liso-cel is preceded by lymphodepleting chemotherapy, most commonly with low-intensity fludarabine and cyclophosphamide to increase the expansion, persistence, and antitumor activity of liso-cel.

The efficacy and safety of liso-cel were demonstrated in Study 017001, conducted under BB-IND 016506, a clinical trial for the treatment of patients with R/R NHL (Abramson, 2020).

Data from Study 017001 in subjects with R/R large B-cell lymphoma, who have failed 2 or more lines of therapy, demonstrate that treatment with liso-cel results in encouraging efficacy outcomes. Among the 256 subjects in the DLBCL Efficacy Set, the overall response rate (ORR) was 73% and the complete response rate (CRR) was 53%. The median duration of response was not reached after a median follow-up of 12 months (95% CI 11.2 to 16.7 months); 60.4% of responders were still in response after 6 months (95% CI: 52.6 to 67.3), and 54.7% after 12 months (95% CI: 46.7 to 62.0). The OS in complete responders has not been reached with a median follow-up of 17.6 months and was 21.1 months (95% CI: 13.3 to NR) for the overall population.

In the safety population, among 269 subjects treated with liso-cel, CRS of any grade was reported in 113 (42%) subjects and 6 (2%) subjects had Grade  $\geq$  3 CRS. Investigator-identified neurotoxicity of any grade was reported in 80 (30%) subjects; 23 (9%) subjects had Grade 3 neurotoxicity and 4 (1%) subjects had Grade 4 neurotoxicity. No Grade 5 CRS or neurotoxicity occurred.

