## **9 RESEARCH METHODS**

### **9.1 Study Design**

#### **9.1.1 Study Design**

This study is designed as a noninterventional registry-based cohort study that is based on secondary use of data from existing independent registries of patients with R/R DLBCL, PMBCL, and FL3B after 2 or more lines of systemic therapy, treated with liso-cel therapy in the postmarketing setting, which includes patients treated with OOS product.

Data from at least [REDACTED] patients with a target of [REDACTED] patients – of which a minimum of [REDACTED] patients will come from European countries – will be collected until death or withdrawal of consent or up to 15 years, whichever occurs first.

This PASS is expected to require up to 5 years to select the planned number of patients globally.

This study is a single-cohort study in which all patients are exposed to liso-cel. Hence, its design does not involve any hypothesis testing regarding a potential difference (in safety or effectiveness) between exposed and unexposed patients.

Secondary malignancies must be reported to the MAH by the treating physicians in order to expedite AE reporting. In the event that a secondary malignancy of T cell origin is suspected, the MAH should be contacted to obtain instructions on the collection and transfer of a tumor tissue

sample for testing in a separate process, outside of this PASS. In the postmarketing setting, the MAH will offer transgene assay service testing for all secondary malignancies of suspected T cell origin where a sample is available, as a routine pharmacovigilance measure to ensure gathering the most information possible for clinical assessment of the reported spontaneous case.

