### **9.2.1 Eligibility Criteria**

All patients who meet the following inclusion criterion will be selected from the registries:

- Patient must have been treated with at least 1 infusion of liso-cel in the postmarketing setting. Patients treated with OOS product will also be eligible.

Patients who meet the following exclusion criterion will not be eligible for selection from the registries:

[figure not shown]
- Patients known to be participating in investigational studies at the time of liso-cel infusion.

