**Table 3: Variables**

Classification	Category	Variable	Description
		Infused dose Diagnosis Date Last Contact Date Safety Assessment Date Effectiveness Assessment Date	Total number of cells or volume infused for each of the CD8+ and CD4+ cell components Date when primary disease was diagnosed Date when patient was the last time in contact with the SC Date of any safety assessments finding (as listed in the safety section) Date of any effectiveness assessments finding (as listed in the effectiveness section)
Baseline	Demographics	Age Weight Height Sex Country Region	Age at infusion (years) Body weight at infusion (kg) Body height at infusion (cm) Sex of patient Country of the infusion center Region of treatment: North America/Europe/Japan/Rest of the World
Baseline	Clinical Variables (Disease History/ Prior Therapy/ Infusion Related)	Karnofsky Performance Score ECOG Performance Score Disease History/Comorbidity Prior Therapy 1 Lines Prior Therapy 2 List Prior Therapy 3 HCT Prior Therapy 4 HCT Type Disease Status 1 Primary Disease	Karnofsky performance score at infusion ECOG performance score at infusion Comorbidity and organ impairment (eg, cardiac, hepatic, obesity, pulmonary, renal, diabetes, solid tumor, and others) at infusion Number of prior therapy lines Names of prior therapies (systemic therapies, standard regimens, including anti-CD19 therapy) Number of prior HCTs Types of prior HCTs (eg, autologous, allogeneic) Primary disease (eg, NHL) and disease status (eg, relapsed or refractory) at infusion

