## 9.7.4 Effectiveness Analysis

### 9.7.4.1 Analysis of the Secondary Effectiveness Endpoints

- **Overall response rate (ORR):** ORR is the proportion of patients with a best overall response of complete response (CR) or partial response (PR), where best overall response is defined as the best disease response recorded from liso-cel infusion until disease relapse or progression or start of new anti-cancer therapy, whichever happens first. If best response is collected by both computerized tomography (CT) and positron emission tomography (PET) methods, best response per PET overrules best response per CT.
- **Complete response rate (CRR):** CRR is the proportion of patients with a best overall response of CR, where best overall response is defined as the best disease response recorded from liso-cel infusion until disease relapse or progression or start of new anti-cancer therapy, whichever happens first. If best response is collected by both CT and PET methods, best response per PET overrules best response per CT.
- **Duration of response (DoR):** DoR is defined as the time from the date of first documented disease response (CR or PR) to the date of first documented progression or first documented relapse, or to date of death due to primary disease, whichever happens first. Patients who are alive and didn't experience disease progression, relapse or death due to primary disease before last contact date will be censored at that time, but no censoring will be done for additional treatment.
- **Progression-free survival (PFS):** PFS is defined as the time from the date of first liso-cel infusion to the date of event defined as the first documented relapse or progression or death due to any cause, whatever happens first. Patients who did not reach such events before the last contact date will be censored at that time, but no censoring will be done for additional treatment.
- **Overall survival (OS):** OS is defined as the time from the date of first infusion to the date of death due to any cause. All patients will be followed for survival information, regardless of whether they receive additional treatment postinfusion. Patients who are alive at last contact date will be censored at that time, but no censoring will be done for additional treatment. OS will be calculated according to the formula:  
$$\text{OS (months)} = (\text{date of death or censoring} - \text{infusion date} + 1) / 30.4375.$$

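### ORR and CRR do not require active disease at infusion, so any patient infused in CR whose CR is recorded again would count as a liso-cel responder

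*Protocol*

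**What the plan says.** Section 9.7.4.1 fixes the numerator and the time window of both response endpoints. For ORR, "ORR is the proportion of patients with a best overall response of complete response (CR) or partial response (PR"). For CRR, "CRR is the proportion of patients with a best overall response of CR". Best overall response is the "best disease response recorded from liso-cel infusion until disease relapse or progression or start of new anti-cancer therapy, whichever happens first", with PET taking precedence over CT. DoR starts at the first documented CR or PR. None of these definitions refers to disease status at infusion.

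The selection rule in section 9.2.1 is short: "Patient must have been treated with at least 1 infusion of liso-cel in the postmarketing setting". The one exclusion is "Patients known to be participating in investigational studies at the time of liso-cel infusion". In section 9.7.1 the Infused Set adds that baseline and disease classification data exist, and the Safety and Effectiveness Set (SES) adds that some postinfusion safety or effectiveness information exists. No response-evaluable set is defined.

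Table 3 does collect the relevant variable: "Primary disease (eg, NHL) and disease status (eg, relapsed or refractory) at infusion". Its only stated use, in section 9.7.3, is a baseline frequency count.

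**The concern.** A response rate is read as the share of patients whose lymphoma responded to the product. That reading needs disease present at infusion. Table 3 lists separate dates for leukapheresis, manufacturing, product receipt, lymphodepletion and infusion, so there is an interval before infusion. Section 9.2 says patients are treated according to real-world practice, so the protocol does not control disease status at the end of that interval.

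If a patient reaches infusion in CR and the 100-day form records CR, the stated rule credits that CR to liso-cel. ORR and CRR would then mix induced responses with remissions carried over from earlier treatment. Sections 8.2.2 and 9.7 carry the same endpoints into subgroups, including regions. If the share of patients in CR at infusion differs between subgroups, their response rates would differ for a reason unrelated to liso-cel.

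**Working it through.** **Does any rule remove the patient?** Take a patient infused in CR, with CR recorded at 100 days and no relapse, progression or new therapy before then.

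- Section 9.2.1: eligible, since the patient had one postmarketing infusion and was in no investigational study.
- Section 9.7.1: in the Infused Set and the SES, provided baseline, classification and postinfusion data exist.
- Section 9.7.4.1: the best response recorded within the window is CR, so the patient counts in both ORR and CRR. The DoR clock also starts.

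No rule in the protocol removes this patient.

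**How large could the effect be?** The protocol gives no target or assumed value for ORR or CRR in this study, so there is no planned figure to reproduce. The inputs for an illustration are:

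- p, the rate in patients with active disease: 73% for ORR and 53% for CRR, from the background in section 7.2.3 ("Among the 256 subjects in the DLBCL Efficacy Set, the overall response rate (ORR) was 73" per cent). These serve only as plausible values.
- f, the share of the denominator in CR at infusion: not in the documents. Assumed 5–10%, with 2% and 20% as outer values.
- q, the chance that such a patient has the remission recorded again within the window: not in the documents. Assumed 1.0 or 0.8.

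Reported rate = (1 − f)p + fq, so inflation = f(q − p).

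| f | q | CRR reported | CRR rise (points) | ORR reported | ORR rise (points) |
|---|---|---|---|---|---|
| 2% | 1.0 | 53.9% | 0.9 | 73.5% | 0.5 |
| 5% | 1.0 | 0.95 × 0.53 + 0.05 = 55.4% | 2.4 | 0.95 × 0.73 + 0.05 = 74.4% | 1.4 |
| 10% | 1.0 | 0.90 × 0.53 + 0.10 = 57.7% | 4.7 | 0.90 × 0.73 + 0.10 = 75.7% | 2.7 |
| 20% | 1.0 | 62.4% | 9.4 | 78.4% | 5.4 |
| 10% | 0.8 | 0.90 × 0.53 + 0.08 = 55.7% | 2.7 | 0.90 × 0.73 + 0.08 = 73.7% | 0.7 |

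The rate is inflated whenever q exceeds p. For the same f and q, CRR is affected more than ORR because its p is lower.

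**Subgroups.** Suppose two subgroups share the same p, with f = 0 in one and f = 10% in the other. At q = 1 their reported CRRs differ by 0.10 × (1 − 0.53) = 4.7 points with no difference in effect.

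**The case against.** The strongest reply is that the protocol nowhere says a patient is infused in remission. Section 9.1.1 describes the source as "existing independent registries of patients with R/R DLBCL, PMBCL, and FL3B after 2 or more lines of systemic therapy", and the examples given for disease status at infusion are relapsed and refractory. This stands as a limit on the claim. A reader might infer that carried-over remissions are in fact being counted, but the documents support only that they would be counted if they occur. The description of the cohort does not close the gap, because section 9.2.1 does the selecting and a relapsed patient can be in remission on the day of infusion.

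Second, section 9.7.4.1 names no denominator and an SAP is to follow. That is right, so it would be too strong to say the rates are fixed in all infused patients, or that any later CR or PR counts, since the window closes at relapse, progression or new therapy. But the numerator and window are stated in full, and an SAP that applied them as written would carry the gap forward.

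Third, disease status will be tabulated, with patient listings, and the subgroup list is open-ended. The share affected may therefore be visible, which lowers the stakes. It does not change what the reported ORR and CRR would mean.

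Fourth, the study is descriptive, with no comparator, and these are two of six secondary endpoints in a safety study. PFS, OS and TTNT run from infusion and do not use the response definition. This also stands. A reader might infer that the results could not be read against 73% and 53%, but the protocol plans no such comparison.

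**Conclusion.** The point holds conditionally. As written, a patient in CR at infusion whose CR is recorded again within the window is a liso-cel responder, and nothing in the eligibility criteria or analysis sets prevents that. With p at the background rates, q = 1 and f = 5–10%, the rise is about 2.4–4.7 points for CRR and 1.4–2.7 for ORR. At q = 0.8 and f = 10% it is about 2.7 and 0.7 points. Both f and q are assumptions, and if no patient is infused in CR the effect is nil.

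Three further inferences are not supported:

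- That DoR is biased upward. The clock would start in these patients, but nothing in the documents shows whether their remissions last longer or shorter than induced ones.
- That the pivotal study restricted its Efficacy Set of 256, out of 269 treated, by disease status. Section 7.2.3 does not explain the difference.
- That patients in PR at infusion should count only if they convert to CR. They have residual disease, and calling every stable PR a non-response could push ORR down. The figures above cover CR at infusion only.

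The change is worth making because it is cheap and removes an ambiguity from two named endpoints.

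**What to change.** First confirm with the registry holders that the coding of disease status at infusion separates remission from active disease, since the examples in Table 3 do not show this. Then state in section 9.7.4.1, and carry into the SAP, that ORR, CRR and DoR are reported in SES patients with active disease at infusion, including those in PR. Present patients in CR at infusion separately, with their number. Keep PFS, OS and TTNT in all patients.

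The cost is a few lines of wording and one flag derived from a variable already collected. The response denominator becomes smaller and the reported rates would probably be slightly lower. The flag also depends on baseline data that section 9.7.3 says are reported retrospectively and only once, so the number of patients with missing status should be shown alongside.

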- **Time to next treatment (TTNT):** TTNT is defined as the time from the date of liso-cel infusion to next treatment of the primary disease (excluding consolidation and maintenance therapies). Patients who did not receive any new treatment for the primary disease before the last contact date or before death will be censored at the last contact date or death date. TTNT will be calculated according to the formula:  
$$\text{TTNT (days)} = \text{date of start of the next therapy line or censoring} - \text{infusion date} + 1$$
- **Time-to-Event (TTE) Analysis:** For DoR, PFS, OS, and TTNT, Kaplan-Meier (KM) estimates and the associated 95% CIs of the median, 25th and 75th percentile will be presented. The 2-sided 95% CIs will be computed using the log-log transformation. The survivor function will be displayed graphically using a KM curve.

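### Duration of response gives no status to responders who die of another cause, and its responder set is not tied to the one used for ORR

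*Protocol*

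**What the plan says.** All the relevant rules stand in Protocol Section 9.7.4.1.

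- **DoR start:** "DoR is defined as the time from the date of first documented disease response (CR or PR"). No cut-off at new therapy is given, and there is no reference back to the ORR definition.
- **DoR event:** progression, relapse, "or to date of death due to primary disease, whichever happens first".
- **DoR censoring:** "Patients who are alive and didn't experience disease progression, relapse or death due to primary disease before last contact date will be censored" at that date, "but no censoring will be done for additional treatment".
- **PFS event:** "first documented relapse or progression or death due to any cause, whatever happens first". PFS is not censored for additional treatment either.
- **TTNT:** patients who die before a next treatment are explicitly censored at death.
- **ORR and CRR:** the window for best overall response closes at relapse, progression or the start of new anti-cancer therapy.
- **Estimator:** "For DoR, PFS, OS, and TTNT, Kaplan-Meier (KM) estimates and the associated 95% CIs of the median, 25th and 75th percentile will be presented".

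Section 9.7.5.1 names the cumulative incidence function for competing risks, but only for the primary safety endpoints. Section 9.3 (Table 3) collects one primary and up to four contributing causes of death. Follow-up runs for up to 15 years (Section 9.1.1).

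**The concern.** A Kaplan-Meier analysis needs an event or a censoring time for every patient. The DoR rules supply neither for a responder who dies in remission, for instance of an infection or a second cancer. PFS, OS and TTNT in the same section have no such gap. Long-term effectiveness is the first secondary objective (Section 8.2.2) and DoR is its measure of durability. Infections and secondary malignancies are among the primary safety endpoints, so some of the deaths without a rule may come from the very events this study is set up to observe.

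Whoever programs the analysis must choose a rule. The choice moves the reported percentiles, and under a disease-specific event the result also depends on how each centre attributes a death. Separately, a DoR denominator that differs from the ORR responders would make the two endpoints hard to read together.

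**Working it through.** **Step 1. Status of each type of responder**

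| Responder's course | DoR | PFS | TTNT |
|---|---|---|---|
| Relapse or progression | event | event | event if next treatment starts |
| Death from lymphoma | event | event | censored at death if no new treatment |
| Alive, none of these | censored at last contact | censored at last contact | censored at last contact if no new treatment |
| Death from another cause, no relapse | **no rule** | event | censored at death if no new treatment |

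**Step 2. What censoring those deaths would estimate**

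The protocol has no planned DoR figure to reproduce, so this is an illustration.

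*Inputs from Section 7.2.3 (Study 017001):* 60.4% of responders still in response at 6 months (95% CI 52.6 to 67.3) and 54.7% at 12 months. One constant hazard through the 12-month value would imply √0.547 = 74.0% at 6 months, outside that interval, so two pieces are fitted:

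- months 0 to 6: h1 = −ln(0.604)/6 = 0.0840 per month
- months 6 to 12: h2 = −ln(0.547/0.604)/6 = 0.0165 per month

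*Assumptions:*

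- these values describe relapse, progression or disease death (the protocol does not say how that study treated other deaths)
- after month 12 the hazard is 0.5 × h2 = 0.00826 per month (1 × and 0.25 × also tried)
- other-cause death is independent, at rate r of 1%, 3%, 5% or 10% per year, with d = r/12 per month

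*Formulas at 60 months:*

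- Other-cause deaths censored: S = 0.547 × exp(−48 × 0.00826) = 36.8%, whatever r is.
- Any-cause death as event: S × exp(−5r).
- Competing risk: 1 − CIF, where CIF sums, over the three periods, h/(h + d) × (fall in the any-cause curve over that period).

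| r per year | Censored | Any-cause | Difference, points | 1 − CIF |
|---|---|---|---|---|
| 1% | 36.8% | 35.0% | 1.8 | 37.4% |
| 3% | 36.8% | 31.7% | 5.1 | 38.7% |
| 5% | 36.8% | 28.7% | 8.1 | 39.8% |
| 10% | 36.8% | 22.3% | 14.5 | 42.5% |

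CIF for r = 10%: 0.387 + 0.053 + 0.135 = 0.575, so 1 − CIF = 42.5%.

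The censored and any-cause curves differ by the factor exp(5r), which runs from 1.05 to 1.65. Over all three tail assumptions the difference at 60 months is about 1 to 18 points.

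*Sign.* The censored curve is never below the any-cause curve. It is below 1 − CIF, here by 0.6 to 5.7 points, because Kaplan-Meier assumes that patients who died would have gone on to relapse at the rate of those still at risk.

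**Step 3. The responder set**

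The ORR window closes at new therapy; the DoR start has no such limit. Consider two patients whose first CR or PR comes after new therapy.

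- *No progression beforehand:* not an ORR responder, but fits the literal DoR start.
- *Progression beforehand:* the first progression precedes the first response, so the literal DoR is negative.

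The protocol gives nothing from which the number or the durations of such responses could be computed.

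**The case against.** Four points can be made in defence of the plan.

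1. *A disease-specific DoR is a legitimate choice and need not match PFS.* This stands. The difference from PFS is not in itself an error, and other-cause deaths are visible in PFS and OS. It does not supply the missing rule for those deaths within DoR.

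2. *The SAP will settle it.* Section 9.7 promises a detailed SAP, and censoring conventions are often completed there. Here, though, the protocol itself states the event and the censoring rule, and the pair is incomplete. An SAP that follows it faithfully inherits the gap.

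3. *The curve is not shown to be overstated.* A reader might infer that DoR will simply look too good. The documents do not support that: they do not say that other-cause deaths are censored, and even if they are, the curve is high only against an any-cause DoR. Against a competing-risk estimate of the protocol's own event it is low.

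4. *Responses after new therapy are not admitted.* A reader might infer that they are. The text only fails to repeat the ORR cut-off, and the negative duration in Step 3 suggests that the ORR meaning of response was intended. What remains is ambiguity for a patient who starts new therapy without progression and then responds. Omitting censoring at additional treatment is consistent with PFS and is not a fault.

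**Conclusion.** The gap is real: a responder who dies of another cause without relapse has no valid status in the planned DoR analysis. Censoring such deaths, the one handling within Kaplan-Meier that fits the event definition, gives a curve that corresponds neither to an any-cause DoR nor to the observable risk of losing response to lymphoma. It also rests on registry cause-of-death attribution. The possible mismatch with the ORR responders is a separate inconsistency with no fixed direction.

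The direction against an any-cause DoR follows from the definitions. The size does not. The figure of roughly 2 to 15 points at 60 months rests on assumed other-cause death rates of 1% to 10% per year, an assumed halving of the hazard after month 12, and independence of the two causes.

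DoR is one of six secondary effectiveness endpoints (Section 9.1.1.2) in a descriptive study, and no test or sample size depends on it. This should be fixed before the first analysis, but it does not affect the primary safety results.

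**What to change.** In Section 9.7.4.1:

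- Restrict DoR to ORR responders, that is, patients whose best overall response before relapse, progression or new anti-cancer therapy is CR or PR. Start the clock at the first such CR or PR.
- Count relapse, progression or death from any cause as the event, as PFS does. Censor patients who are alive without an event at last contact.
- If disease-specific durability is also wanted, report the cumulative incidence of relapse, progression or disease death with other-cause death as a competing event, using the method already named in Section 9.7.5.1. State which cause-of-death entry decides the attribution.

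The cost is one revised definition and, if the disease-specific view is kept, one extra output. The data are already among the variables in Section 9.3. The reported DoR may be somewhat shorter than under the present wording.

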## **9.9 Limitations of the Research Methods**

As this is an observational PASS based upon secondary use of data, sporadic missing data are inevitable, because certain variables may not have been routinely recorded in the patient medical charts. Furthermore, data will also be missing due to gaps in the follow-up (as routine scheduled visits cannot be mandated in an observational study), and loss to follow-up, especially in this study

with a planned duration of 15 years. Details of how missing data are handled are also outlined in the SAP.

The above-mentioned potential issue can lead to significant biasing effects on time to event analyses, as well as analyses quantifying a duration. In the EBMT and the CIBMTR registries, data are recorded at baseline, 100 days, 6 months, and then yearly. Thus, owing to center-specific different levels of compliance, a high variability in the recording of assessment dates is to be expected.

To minimize selection bias, treatment centers will be encouraged to include patients in the registries and will be requested to ask every patient treated with liso-cel to share data with the registry. The MAH has implemented a healthcare professionals (HCPs) educational program in Europe that informs HCPs that patients who receive liso-cel are expected to be enrolled in a registry and to be followed in the registry in order to better characterize the long-term safety and effectiveness profile of liso-cel. In addition, the registry holders will provide continuous support and regular training to the treatment centers and will maintain constant contacts with them, emphasizing the importance and purpose of the data collection, and encouraging them to enter baseline patient data promptly and to capture follow-up data continuously. The registry holders will compensate participating treatment centers for data entry into the registries.

Nevertheless, not all patients will consent to have their data sent to the EBMT or the CIBMTR registries, possibly resulting in a biased sample of patients. A high rate of attrition (particularly if mortality is not captured well) could bias the results. In addition, in order to monitor the reporting, the study team will reconcile shipped products to each center participating in the study with the subsequent compliance of the patient and center with the study.

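### PFS and DoR are censored at last contact, so time after disease assessment stops counts as progression-free and both can be biased upward

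*Protocol*

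**What the plan says.** Section 9.7.4.1 defines a PFS event as "first documented relapse or progression or death due to any cause, whatever happens first", and for patients without one it states: "Patients who did not reach such events before the last contact date will be censored at that time". The DoR event is "first documented progression or first documented relapse, or to date of death due to primary disease, whichever happens first". Living responders without progression, relapse or "death due to primary disease before last contact date will be censored at that time". OS is also censored at last contact, so one date serves both survival and the progression endpoints.

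Table 3 lists two separate dates. Last Contact Date is the "Date when patient was the last time in contact with the SC". Effectiveness Assessment Date is the "Date of any effectiveness assessments finding (as listed in the effectiveness section").

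Section 9.9 says that "data are recorded at baseline, 100 days, 6 months, and then yearly" and that "routine scheduled visits cannot be mandated in an observational study". It expects follow-up gaps and variable recording of assessment dates, and it accepts that time-to-event analyses may be biased, without giving a direction. The ENCePP checklist (Appendix 2, item 10.8) answers No on sensitivity analyses.

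**The concern.** Progression and relapse count only once they are documented. A patient who is still in contact with the site but no longer has disease assessments cannot have a progression recorded, yet stays in the Kaplan-Meier denominator until last contact. The unassessed time is treated as known to be progression-free. Last contact is a sound censoring date for OS, because any contact establishes that the patient is alive. It does not establish that the disease has not progressed.

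Long-term effectiveness is a secondary objective, and the plan reports Kaplan-Meier medians and quartiles for both endpoints. An upward bias would go straight into those figures.

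**Working it through.** **No figure to reproduce.** The protocol gives no event count, target or precision for PFS or DoR. It also does not say how often contact outlasts disease assessment. Size can only be shown under assumptions.

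**Direction.** Let λ(t) be the true hazard of progression or death, and u(t) the share of the risk set that is in contact but no longer assessed. In that share, progressions go unrecorded and only later deaths can appear. If deaths are set aside, the estimated hazard is about λ(t)·[1 − u(t)], which is below λ(t) whenever u(t) > 0. With u(t) = 0 there is no bias.

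**Model A (all inputs assumed).** 100,000 patients per run.
- 45% are long-term progression-free (progression mean 400 months); the rest progress with mean 4.5 months.
- Death from other causes has mean 500 months; survival after progression has mean 8 or 24 months.
- Assessments fall at 100 days, 6 months and then yearly, as in section 9.9.
- Last contact is uniform over 24-84 months.
- In a share f of patients, assessment stops at a random time within 0-24 months while contact continues.
- Deaths up to last contact count as PFS events under both censoring rules.

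Check on the true value at 12 months: [0.45·e^(−12/400) + 0.55·e^(−12/4.5)]·e^(−12/500) = (0.4367 + 0.0382) × 0.9763 = 46.4%. The simulated true values are 46.2-46.5%. Simulation error per estimate is about √(0.46 × 0.54/100,000) = 0.16 points.

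PFS in %, as true / last-contact rule / last-assessment rule:

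| Mean survival after progression | f | 12 months | 36 months |
|---|---|---|---|
| 8 months | 0% | 46.3 / 46.3 / 46.3 | 38.3 / 38.3 / 38.1 |
| 8 months | 10% | 46.2 / 46.9 / 46.3 | 38.1 / 38.2 / 36.8 |
| 8 months | 20% | 46.5 / 47.7 / 46.5 | 38.4 / 38.7 / 35.8 |
| 8 months | 40% | 46.5 / 48.9 / 46.5 | 38.4 / 38.9 / 32.6 |
| 24 months | 0% | 46.3 / 46.3 / 46.3 | 38.1 / 38.1 / 38.0 |
| 24 months | 10% | 46.3 / 47.2 / 46.5 | 38.3 / 38.9 / 37.4 |
| 24 months | 20% | 46.5 / 48.4 / 47.0 | 38.3 / 39.5 / 36.4 |
| 24 months | 40% | 46.4 / 50.3 / 47.5 | 38.2 / 40.8 / 34.0 |

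At 12 months, last-contact minus true is +0.7 to +0.9 points at f = 10%, +1.2 to +1.9 at 20% and +2.4 to +3.9 at 40%.

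A DoR-type endpoint, on which only disease deaths count, moved by a similar amount here: 51.4% against a true 47.5% at 12 months (f = 40%, 24-month setting). Its median was 18.3 months under last-contact and 12.0 under last-assessment censoring. That median is fragile, because the curve is flat near 50%. Both values also exceed the true 9.8, partly because progression is detected only at visits, which is a separate matter.

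**Model B (all inputs assumed).** Progression hazard is 5% per month in year 1 and 1.5% after, with a Year-5 cut. True PFS is e^(−0.60) = 54.9% at 12 months and e^(−0.60−0.36) = e^(−0.96) = 38.3% at 36 months. With contact trailing assessment in 10-20% of patients, and deaths counted (mean survival after progression 4.4-24 months), the last-contact rule gives 55.1-55.6% at 12 months (+0.2 to +0.7) and 38.5-39.1% at 36 months (+0.2 to +0.8).

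**Does moving the date cure it?** At 12 months the last-assessment rule is within about 1 point of the truth. At 36 months in Model A it is too low: by 0.9 to 1.3 points at f = 10% and by 4.2 to 5.8 at 40%. That error is larger than the last-contact error in the same runs. Patients with a gap who die are counted as events, while those who do not die leave the risk set early. Changing the date without a rule for events after a gap is therefore not enough.

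**The case against.** The strongest reply is that the gap is inferred. Table 3 puts relapse and progression outcomes and survival status at last contact in the same outcome block, reported on the same schedule, and contact means contact with the centre that infused the patient. If disease status is updated at every such report, the two rules agree to within about 0.2 points. This stands as a limit on size. It does not remove the point: nothing requires a disease status at last contact, and section 9.9 expects gaps.

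It also stands that deaths partly protect PFS, since any death after an unrecorded progression is an event. DoR has less protection, because deaths from other causes do not count, although the runs above show little difference between the two endpoints at 12 months.

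Section 9.9 leaves missing-data handling to the SAP, which is not shown and may add to this. The censoring date itself, however, is fixed in the protocol.

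Three stronger readings are not supported.
- A reader might infer a large inflation from a run in which every patient has a gap and deaths are ignored. Model B then gives 56.8% or 59.3% against 54.9% at 12 months, for gaps of up to 6 or 12 months. The protocol does not suggest that every patient has a gap, and its PFS definition counts deaths.
- A reader might expect worse at an early data cut. The interim reports are at Years 5, 10 and 15; the earlier outputs listed are safety reports and progress updates.
- A reader might infer that regional results are distorted. Section 9.9 describes compliance as differing by centre; nothing says that gaps differ by registry or region, and subgroup results are descriptive.

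**Conclusion.** The point holds as a conditional bias. The rule in section 9.7.4.1 biases PFS and DoR upward to the extent that contact outlasts disease assessment, and the protocol neither excludes such gaps nor plans a sensitivity analysis for them. Under the assumed models the effect on 12-month PFS is nil with no gaps, roughly 0.2 to 2 points with gaps in 10-20% of patients, and up to about 4 points at 40%. None of these shares comes from the documents. The change is worth making before the Year-5 interim report. It touches secondary, descriptive endpoints only; the primary safety endpoints and the study size are unaffected.

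**What to change.** Amend section 9.7.4.1 as follows.

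- Censor PFS and DoR at the last date on which a disease assessment recorded no relapse or progression. If there is none, use the infusion date for PFS and the first-response date for DoR.
- Define that date from CT, PET or the relapse/progression outcome. Effectiveness Assessment Date cannot be used as it stands, because the effectiveness block of Table 3 also contains survival status and cause of death.
- State how a progression or death after missed assessments is handled. This is what governs the late-time bias shown above.
- While rewriting the DoR sentence, state what happens to responders who die of another cause; the present sentence covers only patients who are alive.
- Keep last contact for OS.
- Report the present last-contact rule alongside as a sensitivity analysis. In the Model A runs with gaps, the two rules lay on either side of the truth at 36 months; at 12 months both were at or slightly above it. The pair indicates a range, not a guaranteed bracket.

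The cost is protocol wording, a derived date from variables already collected, and a second set of Kaplan-Meier outputs. The statistical cost is less follow-up time, wider late confidence intervals, and a possible downward bias at late times where deaths after a gap still count.
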